To evaluate the impact of PACTS on surgical residents' knowledge and attitudes about caring for diverse patients, we will use a pre- and post-test in the form of validated instruments that assess knowledge, attitudes, and self-reported skills on a Likert-type scale. This pre- and post-test will be piloted among a group of surgical residents (N=40) to assess the survey length and clarity of questions. Residents will be recruited using a convenience sampling method from those who participated in the surgery focus groups at ASC 2019. Exclusion criteria from this pilot will be residents at one of the trial AMCs.

Resident skills will also be objectively assessed through an Objective Structured Clinical Examination (OSCE) that will be created by the study

staff and administered immediately before the intervention and within 1-6 months after the intervention has been completed. The OSCE uses 5-point Likert scale questions to evaluate resident performance across multiple domains. A Standardized Patient evaluator and a third-party trained impartial observer will evaluate the residents on these domains, and the resulting numerical scores will be averaged. It will serve both a summative and educational purpose in this context. Due to the COVID-19 pandemic, in order to adhere to social distancing protocols, the OSCE may also be delivered virtually using a secured web-based video-conference software.

We have also developed a novel survey instrument to assess resident knowledge, attitudes, and self-reported skills. This instrument is adapted from pre-existing, validated instruments such as the Cultural Competence Health Practitioner Assessment (CCHPA), developed by the National Center for Cultural Competence, and modified to be relevant to surgical training and practice. Residents will be required to take a knowledge survey before and after receiving the PACTS curriculum or standard training. Attitudes regarding the importance of facing cross-cultural health care situations will be assessed across multiple domains using a novel survey instrument that is based on a survey that was used in a similar curriculum aimed at medical students, as well as the Values and Belief Systems domain.

Patients

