Pre- and post-intervention patient-reported satisfaction and NSQIP outcomes. Management of pain will be assessed using elements of the Pain Treatment Satisfaction Scale (PTSS).¹⁴⁰ Previous work by Gupta et al suggests that, on average, 63% of patients provided assessments of pain control satisfaction in the upper quintile of a standardized 10-point satisfaction scale.¹⁴¹ Subsequent to the intervention, it is estimated that 73% of patients treated by PACTS-trained residents will report satisfaction in the uppermost PTSS quintile. We expect an 8% decrease in readmissions, from 23% to 15% post-intervention. Pre-post intervention differences in patient-reported satisfaction and NSQIP outcomes will be assessed using Chi-square, Fisher's exact tests, or t-tests as appropriate, and ordinal scale differences will be assessed using Chi-Square tests and ordered logistic regression, both without adjustment and controlled for patient-, clinician-, and facility-level factors. It is important to note that the patient groups represent independent samples, and these pre- and post-intervention measures are independent measures, not repeated measures (Table 8). To achieve this, we will recruit 100 patients per site for each data collection phase. Thus, we will collect 300 patients per site over the entire study (2,400 total), giving ample power for both patient and clinical outcomes.

Table 7. Sample Size Calculations

Example Measure	Proportional Difference to be Measured	Expected Minimum Number of Participants Per Group	Minimum Detectable Difference (80% power and $\alpha=0.05$)
Sample size/power calculations for repeated measures			
Within group resident knowledge/skills/attitudes	Pre- vs. Post-test proportion achieving "Adequate" vs. "sub-optimal" dichotomized assessments	Pre-intervention: 160 Post-intervention: 160 (Repeated Measures)	Pre-intervention: 50.0% Post-intervention: 61.0% Thus, we expect to be able to detect a proportional absolute difference of 11% for within-group assessments.
Sample size/power calculations for independent measures.			

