Between group resident knowledge/ Skills/attitudes	Post-test proportion in Early Group vs. Delayed Group achieving "adequate" vs. "sub-optimal" dichotomized assessments	Early Group: 159 Delayed Group: 159 (Independent Measures)	Change from 50% to 65.5% Assuming remains at 50% with no change from baseline assessment. Thus, we would be able to detect a 15% relative proportional difference between groups associated with exposure to PACTS training.
Patient-reported within and between-group differences			
Patient-reported outcomes	Pre- vs. Post-test proportion of patients reporting pain-satisfaction scores in the uppermost standardized quintile	Pre-intervention: 361 Post-intervention: 361 (Independent Measures)	Proportion of Patients with scores Pre-intervention: 63.0% Post-intervention: 73.0% Thus, we expect to be able to detect an absolute proportional difference of 10%.
Sample size/power calculation for NSQIP outcomes			
Readmissions	Pre- vs. Post-test proportion of patients readmitted	Pre-Intervention: 377 Post-intervention: 377	Proportion of Patients readmitted Pre-intervention: 23% Post-intervention: 15%

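### Table 7 powers the resident outcomes on an undefined 'adequate' cut of multi-item scores, and the SAP does not say whether that cut, chi-square or ordered logistic regression decides

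*SAP*

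**What the plan says.** **What is collected.** The protocol (study procedures, Residents) describes 5-point OSCE items over several domains, scored by two raters: "A Standardized Patient evaluator and a third-party trained impartial observer will evaluate the residents on these domains, and the resulting numerical scores will be averaged". Knowledge, attitudes and self-reported skills come from Likert-type surveys given before and after training.

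**What is powered.** Both resident rows of SAP Table 7 use a yes/no outcome. The within-group row is "Pre- vs. Post-test proportion achieving" an adequate rating, 50.0% to 61.0% with 160 residents. The between-group row is "Post-test proportion in Early Group vs. Delayed Group achieving" it, with 159 per group: "Change from 50% to 65.5% Assuming remains at 50% with no change from baseline assessment".

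**What is to be tested.** For dichotomous repeated measures the SAP names chi-square, Fisher's exact test and logistic regression. For ordinal resident outcomes, within and between groups, it names chi-square plus unadjusted and adjusted ordered logistic regression. The covariates are resident and program factors; the baseline score is not named among them. T-tests appear only for patient-reported and NSQIP outcomes.

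**What is not stated.** Neither document gives the cut-point for *adequate*, a rule for grouping an averaged score into ordered categories, or which listed analysis decides.

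**The concern.** The average of two raters on a single 5-point item already takes nine values (1, 1.5, and so on to 5), and averaging over domains adds many more. Cutting such a score in two discards information that has been paid for. A chi-square test on several categories keeps the categories but ignores their order.

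Resident numbers are set by program size, at about 200 per arm, and there are only 8 sites. Better use of collected scores is one of the few inexpensive ways to gain power. An unstated cut-point and an unranked list of tests also leave room to choose after the data are seen, and power depends on where the cut falls.

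**Working it through.** **Inputs.** From Table 7: 80% power, alpha 0.05 (two-sided reproduces the table; sidedness is not stated), 50% vs 65.5%, 159 per group. From the SAP text: 200 per group less 20% = 160. (1.960 + 0.8416)² = 7.849.

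**1. Reproduce the plan.**
- Between groups, pooled-variance formula, mean rate 0.5775: n = [1.960·√(2·0.5775·0.4225) + 0.8416·√(0.25 + 0.655·0.345)]² / 0.155² = 158.2, so 159. This matches, and power at 159 is 80.2%.
- Within group, one-sample formula against a fixed 50%: n = [(1.960·0.5 + 0.8416·√(0.61·0.39)) / 0.11]² = 159.8, so 160. This matches.

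**2. Same effect on a normal score, cut at the control median** (as the 50% implies), independent residents.
- Shift d = Φ⁻¹(0.655) = 0.399 SD.
- n = 2·7.849 / 0.399² = 98.7, so 99 per arm. Saving (159 − 99)/159 = 38%.
- Power at 159: Φ(0.399/√(2/159) − 1.960) = Φ(1.596) = 94%, against 80%.

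**3. Same effect under proportional odds.** This is the model behind the ordered logistic regression that the SAP lists.
- Odds ratio (0.655/0.345)/1 = 1.90, log 0.641.
- Whitehead's formula: n per arm = 6·7.849 / [0.641²·(1 − Σp̄³)], where p̄ is the mean category probability over the arms.

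| Control categories | Σp̄³ | n per arm | Saving vs two |
|---|---|---|---|
| 2 (median cut) | 0.268 | 156.5 | – |
| 5 equal | 0.044 | 119.9 | 23% |
| 10 equal | 0.011 | 115.9 | 26% |
| 50 equal | 0.0004 | 114.6 | 27% |

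One unequal five-category split (10/20/20/30/20%) gives 121.9, a saving of 22%.

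**4. Chi-square on ordered categories.** The 0.399 SD shift across five equal control categories puts 10.7, 15.0, 18.5, 22.9 and 32.9% of the Early group in them. At 159 per arm the noncentrality is 10.99 on 4 df, so power is 76%. That is below even the binary test's 80%.

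**5. Position of the cut**, same 0.399 SD shift and 159 per arm.
- 20% of controls adequate: Φ(−0.842 + 0.399) = 32.9% in the Early group. Power 74%, or 183 per arm for 80%.
- 80% of controls adequate: Φ(0.842 + 0.399) = 89.3%. Power 63%, or 237 per arm.

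**6. Clustering.** Assume 4 vs 4 sites of 40 residents (160 per arm), a t-test on 6 df, and ICC ρ for the normal score.
- Score: variance of the arm difference = 2(1 + 39ρ)/160.
- Cut: the dichotomy has a smaller ICC. At the median it is (2/π)·arcsin ρ; at 65.5% it comes from the bivariate normal. At ρ = 0.01 these are 0.0064 and 0.0060; at ρ = 0.05, 0.0318 and 0.0302. Variance = [0.25(1 + 39ρ₁) + 0.226(1 + 39ρ₂)]/160.

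| Assumed ρ | Effect/SE, score | Effect/SE, cut | Power, score | Power, cut |
|---|---|---|---|---|
| 0.01 | 3.026 | 2.550 | 71% | 57% |
| 0.02 | 2.674 | 2.333 | 61% | 50% |
| 0.05 | 2.077 | 1.911 | 42% | 36% |

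The information lost by cutting is 1 − (2.550/3.026)² = 29% at ρ = 0.01 and 1 − (1.911/2.077)² = 15% at ρ = 0.05.

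**The case against.** A reader might infer that the SAP cuts the resident scores and tests them only by chi-square. It does not say so. Its between-group paragraph concerns ordinal outcomes, self-reported and observer-assessed, and plans ordered logistic regression with and without adjustment. Table 7 labels its rows as examples, and a binary sizing example does not bind the analysis. An ordinal model can also take a score with many values, and the three- and five-point scales in the SAP are only illustrations. All of this stands: the dichotomy governs Table 7, but not necessarily the final inference.

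A reader might also infer that more than a third of the information is lost outright, or that 99 residents per arm or 94% power is within reach. Both need a normal score, a median cut and independent residents. The documents give no SD, distribution or ceiling for these scores, and sites are randomized, not residents. Steps 3 and 6 show smaller losses and much lower power.

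Finally, the adequate proportion matches the scale of the earlier OSCE evidence that the SAP cites (a 20-25% increase). That is a fair reason to report it, and even to size on it. It does not supply a cut-point or say which test decides. The listed ordered regression also comes with no grouping rule and no named baseline-score term.

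**Conclusion.** The point holds in a limited form. The resident sample size rests on an undefined cut of scores collected in much finer detail. The SAP does not rank its listed tests, and one of them ignores order. It plans no analysis of the averaged score itself and states no adjustment for the baseline score.

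For independent residents the cost of a median cut is about 23-27% of the sample under proportional odds and about 38% under a normal score. This cost falls on the trial's conclusions only if the dichotomized test is taken as decisive, which the SAP leaves open. With clustering the gain is smaller but does not vanish: about 14 points of power at ICC 0.01 and 6 at 0.05, given 4 vs 4 sites of 40 residents and a normal score. The ICCs and the score distribution are assumptions. Analysing the score does not by itself restore 80% power under any of the ICCs shown. The change should be made, but it is a matter of efficiency and pre-specification and does not invalidate the trial.

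**What to change.** Amend the SAP before resident outcomes are compared by arm:

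- Name the mean OSCE score and the survey total scores as the deciding resident outcomes, and state how each is formed across raters, domains and items.
- Analyse the between-group comparison in a linear mixed model with arm, baseline score and a random site effect, with a small-sample correction for 8 sites. If the scores are skewed or at ceiling, use an ordinal model with the same terms, and fix beforehand the rule for switching.
- Keep the adequate proportion as a supportive summary with a pre-stated cut-point.
- Drop chi-square as a deciding test.

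The cost is SAP wording only; no new data are needed. The downside is that the effect is expressed in score points, which are harder to set beside the earlier OSCE evidence. Reporting the adequate proportion alongside deals with that.

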Cover Page for ClinicalTrials.gov

Official Study Title:

Evaluation of a Cultural Dexterity Training Program for Surgeons: The PACTS Trial

NCT Number:

NCT03576495

Document:

Statistical Analysis Plan

Document Date:

June 6, 2017

PACTS ANALYSIS PLAN: The multi-year cluster-randomized study design will enable us to examine differences between and within the Early Intervention and Control/Delayed PACTS training groups across three unique time points (Year 2 pre-intervention, Year 2 post-intervention and Year 3 post-intervention). Details of statistical measures/methods and power calculations appear below.

Within-group differences (repeated measures).

Repeated measure differences on dichotomous outcomes will be examined using Chi-square and Fisher's exact tests, as well as unadjusted logistic regression models controlling for resident-specific demographic factors (e.g. age, IAT, post-graduate year, and sex).

Differences in ordinal outcomes (e.g. three- or five-point Likert scale reporting or ordered category scores) between pre- and post-intervention testing will be examined using Chi-square tests, unadjusted ordered logistic regression, and ordered logistic regression adjusted for resident- and program-specific factors. Table 7 depicts our sample size/power calculations, according to which we will be able to detect an 11% absolute difference in the proportion achieving "adequate" vs. "sub-optimal" dichotomized assessments before and after PACTS training. This accounts for an up to 20% sample loss from the expected 200 enrolled residents per group.

Between-group differences (independent measures). Pre- vs. post- differences in both self-reported and observer-assessed ordinal outcomes between the Early and Delayed Intervention groups will be assessed at the end of the first training period using Chi-square tests and unadjusted ordered logistic regression, as well as ordered logistic regression models controlling for resident- and program-specific factors. Previous work demonstrated that exposure to training similar to PACTS was associated with a 20-25% increase in the proportion of trainees achieving "adequate" scores on an OSCE-based assessment. Based on the number of residents in each arm (n=200), we anticipate that we will be able to detect a much smaller between-group difference even with up to 20% sample attrition over time (Table 7).

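### SAP Table 7 labels the between-group resident effect 15% relative, but its own endpoints are 15.5 points absolute (31% relative), before any allowance for clustering by site

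*SAP*

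**What the plan says.** The between-group resident row of SAP Table 7 gives the group sizes as "Early Group: 159 Delayed Group: 159 (Independent Measures)". It describes the effect as "Change from 50% to 65.5% Assuming remains at 50% with no change from baseline assessment", meaning that the Delayed group is taken to stay at its baseline. The table's column heading sets 80% power and alpha 0.05. The row then concludes: "Thus, we would be able to detect a 15% relative proportional difference between groups associated with exposure to PACTS training".

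The within-group row of the same table uses the other scale: "we expect to be able to detect a proportional absolute difference of 11% for within-group assessments", from 50.0% to 61.0%. The patient-reported row also calls its 10% (63% to 73%) absolute.

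The SAP text on between-group differences refers to this row. It says that training similar to PACTS was "associated with a 20-25% increase in the proportion of trainees achieving 'adequate' scores on an OSCE-based assessment", and that with 200 residents per arm "we anticipate that we will be able to detect a much smaller between-group difference even with up to 20% sample attrition over time". It does not say whether the 20-25% is in percentage points or relative.

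The protocol (Research Design and Methods) describes a cluster-randomised trial at 8 centres, with half the sites in each group.

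**The concern.** A move from 50% to 65.5% is not a 15% relative difference on any reading. Only this row uses the word relative, while its neighbours say absolute, so the word looks deliberate.

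The row covers the comparison of randomised groups in year 1, before the Delayed sites receive PACTS. Its minimum detectable difference is the main statement of what that comparison can show. The scale also decides whether the SAP's comparison with previous work is true, because 15 looks smaller than 20-25 whichever scale is meant. Finally, the row labels the residents as independent measures, although whole sites are randomised.

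**Working it through.** **Inputs.** From SAP Table 7: 50% and 65.5%, 159 per group, 80% power, alpha 0.05. Sidedness is not stated; two-sided reproduces the plan's figure. From the protocol (Resident Recruitment): 200 residents per arm, on average 50 per site. From the SAP: up to 20% loss, so 200 × 0.8 = 160 per arm and 50 × 0.8 = 40 per site. The ICC values are assumptions; the documents give none.

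**Formula.** Two independent proportions, pooled variance under the null, no continuity correction, with p̄ the mean of p1 and p2:

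n per group = [1.960·√(2p̄(1−p̄)) + 0.842·√(p1(1−p1) + p2(1−p2))]² / (p2−p1)²

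**1. The plan's own figure.** For 50% vs 65.5%, p̄ = 0.5775. The numerator is (1.369 + 0.581)² = 3.802 and the denominator is 0.155² = 0.024025. This gives n = 158.2, so 159 per group, an exact match. Power at 159 is 80.2%. No design effect is needed to reach 159, so none was applied.

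**2. The scale.** Absolute: 65.5 − 50 = 15.5 points. Relative: 15.5/50 = 31%.

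**3. What 15% relative would mean.** 50% × 1.15 = 57.5%, a difference of 7.5 points. The numerator is (1.382 + 0.592)² = 3.896 and the denominator is 0.075² = 0.005625. This gives n = 692.6, so 693 per group. Power at 159 is 26.7%.

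**4. Reading the 15% as points.** 50% vs 65% needs 170 per group and has 77.5% power at 159. So 15 is also a rounding down of 15.5, in the favourable direction.

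**5. Clustering.** Design effect = 1 + (40 − 1) × ICC, applied to 160 per arm, with 50% in the Delayed group:

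| Assumed ICC | Design effect | Effective n per arm | Detectable difference at 80% power |
|---|---|---|---|
| 0.01 | 1.39 | 115.1 | 18.1 points |
| 0.02 | 1.78 | 89.9 | 20.3 points |
| 0.05 | 2.95 | 54.2 | 25.7 points |

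At ICC 0.05, power is about 57% for 20 points and 77% for 25 points. These figures assume equal site sizes and make no correction for having only 8 clusters.

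**6. The comparison with 20-25%.**
- If it is absolute, 15.5 is below 20-25 before clustering. After clustering the detectable difference is 18 to 26 points, which is no longer clearly below that range.
- If it is relative, 50% rises to 60% (50 × 1.20) or 62.5% (50 × 1.25). Power at 159 is then about 43% or 61%, even with no clustering. The detectable 31% relative effect is larger than the prior effect, so the SAP's statement is false on this scale.

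**The case against.** The strongest reply is that this is one wrong word. The same cell prints both proportions, the 15 is recognisably 65.5 minus 50 rounded, and nothing in the documents mentions 57.5%. Relative might loosely have meant relative to the Delayed group. Resident numbers rest on programme size and away rotations (protocol, Resident Recruitment), not on this calculation. Most of this stands: 159 is right for its endpoints, and no enrolment or analysis changes. It does not rescue the sentence, which states a figure that the design does not have, beside rows that use the scale correctly.

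Two stronger readings are tempting, and the documents do not support them. A reader might infer that the table's rows cannot be compared. They can, because both resident rows print their endpoints: 11 points within group and 15.5 between groups. A reader might also infer that, once clustering is counted, the trial could not detect a 20-25% effect. Even if that effect is absolute and the ICC is 0.05, power is about 57% to 77%. That is below the planned 80%, but it is not an inability to detect.

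It is also fair to say that clustering is a separate matter from the label. It belongs here only because a restated detectable difference that left it out would still be too favourable.

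**Conclusion.** The sentence is wrong as written. The row's detectable difference is 15.5 percentage points absolute, or 31% relative. Read literally, the 15% relative label states an effect about half that size (7.5 against 15.5 points), for which power at 159 is about 27% instead of 80%. That twofold gap applies to the sentence taken alone, since the endpoints beside it are correct.

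This part rests only on the SAP's own numbers and a two-sided test. The clustered figures of about 18, 20 and 26 points rest on assumed ICCs and 40 residents per site. They show a direction and a range, and are not estimates for this trial. Whether the SAP's comparison with previous work holds cannot be settled until the scale of the 20-25% is given. If it is absolute, the comparison holds only before clustering; if it is relative, it is false. This is a correction that should be made; it does not put the sample size in question.

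**What to change.** 1. In the between-group row of Table 7, replace the concluding sentence with: a 15.5 percentage-point absolute difference (31% relative), before allowance for clustering by site.
2. Add the cluster-adjusted detectable difference for a stated ICC range, with the assumed number of residents per site. At 40 per site and ICCs of 0.01, 0.02 and 0.05 it is about 18, 20 and 26 points.
3. In the text on between-group differences, state whether the 20-25% increase from previous work is absolute or relative. Then requalify the claim that a much smaller difference is detectable, or delete it if the increase is relative.

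The cost is SAP wording and a less favourable stated sensitivity. No extra residents, patients or analyses are needed.
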